6.6. PrEP Discontinuation

6.6.1. Participants will be deemed as having discontinued PrEP if they miss more than 3 consecutive months for PrEP.

6.6.2. Participants will be called, texted and emailed for three consecutive months before considered them as discontinued.

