6.2.1. Baseline Patient Demographic Survey

6.2.2. Medication Persistence

6.2.2.1. Definition: Continue to take medicines over time independent of adherence to the PrEP medication regimen.

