6.2.3. Persistence Assessment CAB-LA

6.2.3.1. The proportion of participants who received at least one PrEP injection who remained on injectable PrEP or oral bridging at months 3 and 11 measured by the self-report assessment and validated with claims data.

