6.2.4. Persistence Assessment Oral PrEP

6.2.4.1. The proportion of participants who initiated oral PrEP who remained on oral PrEP at months 3 and 12 measured by the self-report assessment and validated with claims data period.

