You are treated with less respect than other people are. 
  Never  Less than once a year  A few times a year  A few times a month  At least once a week  Almost every day 	15
People act as if they're better than you. 
  Never  Less than once a year  A few times a year  A few times a month  At least once a week  Almost every day 	16
What do you think is the main reason for these experiences? (Select 1) 
  Your gender  Your sexual orientation  Your race  Your religion  Some aspect of your physical appearance  Your education or income level  Other: [Write in] 	17

End Message: Thank you for completing this survey!

Persistence Assessment

Activity Title: Are You Still Taking PrEP?

Activity Description: In this short survey, we'll ask you some questions about your PrEP journey and any challenges you may have encountered.

Activity:

1. Are you still getting PrEP medicine by an injection from your healthcare provider?

- Yes, I am taking PrEP ([branching logic to question 4](#))
- No, I stopped taking PrEP ([branching logic to question 2](#))

2. If you stopped taking PrEP, which of the following best describes the reason(s) why?

[Select up to 2]

- I no longer feel I needed to take PrEP ([branching logic to question 3 if selected](#))
- It was too difficult to take to take PrEP as prescribed with my lifestyle
- I felt I was being judged by others for taking PrEP
- I experienced side effects from taking PrEP

- I take too many medications
- There were too many appointments as part of my PrEP care
- I tested positive for HIV
- Other: [Fill in the blank]

3. Which of the following best describes why you no longer feel you need to take PrEP?

- I am no longer having sex
- I am in a monogamous relationship
- I am no longer using injectable drugs
- My partners and I are all regularly using condoms and getting tested for HIV
- Other: [Fill in the blank]

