You are treated with less respect than other people are. 
  Never  Less than once a year  A few times a year  A few times a month  At least once a week  Almost every day 	15
People act as if they're better than you. 
  Never  Less than once a year  A few times a year  A few times a month  At least once a week  Almost every day 	16
What do you think is the main reason for these experiences? (Select 1) 
  Your gender  Your sexual orientation  Your race  Your religion  Some aspect of your physical appearance  Your education or income level  Other: [Write in] 	17

End Message: Thank you for completing this survey!

Persistence Assessment

Activity Title: Are You Still Taking PrEP?

Activity Description: In this short survey, we'll ask you some questions about your PrEP journey and any challenges you may have encountered.

Activity:

1. Are you still taking PrEP medicine by mouth?

- Yes, I am taking PrEP (branching logic to question 4)
- No, I stopped taking PrEP (branching logic to questions 2)

2. Over the past week, how many days did you miss taking PrEP?

- 0
- 1
- 2
- 3
- 4
- 5
- 6

7

3. If you stopped taking PrEP, which of the following best describes the reason(s) why? [Select up to 2]

- I no longer feel I needed to take PrEP (branching logic to question 3 if selected)
- It was too difficult to take PrEP with my schedule
- I did not want people to know I was taking it or I felt I was being judged by others for taking PrEP
- I did not like the side effects
- I take too many medications
- There were too many appointments as part of my PrEP care
- I tested positive for HIV
- Other: [Fill in the blank]

4. Which of the following best describes why you no longer feel you need to take PrEP?

- I am no longer having sex
- I am in a monogamous relationship
- I am no longer using injectable drugs
- My partners and I are all regularly using condoms and getting tested for HIV
- Other: [Fill in the blank]

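### Late persistence is read from a current-status answer, so a participant whom 6.6.1 deems discontinued can still be counted as having stayed on PrEP

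*Combined protocol and SAP*

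**What the plan says.** Section 6.2.2 defines persistence as a matter of continuity: "Continue to take medicines over time independent of adherence to the PrEP medication regimen". Section 6.2.3 makes the CAB-LA endpoint the proportion "who remained on injectable PrEP or oral bridging at months 3 and 11 measured by the self-report assessment and validated with claims data". Section 6.2.4 makes the oral endpoint the proportion "who remained on oral PrEP at months 3 and 12 measured by the self-report assessment", also with claims validation.

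The status comes from one yes/no item: "Are you still getting PrEP medicine by an injection from your healthcare provider" in Appendix B and "Are you still taking PrEP medicine by mouth" in Appendix C. Section 7 compares the self-reported proportions at 3 months and end of study by chi-square or Fisher's exact test. It says MPR will validate self-report, and it compares the percentages with MPR of at least 1.0 as a separate test.

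Section 6.6 contains a different status rule. Section 6.6.1 reads "Participants will be deemed as having discontinued PrEP if they miss more than 3 consecutive months for PrEP", and 6.6.2 adds "Participants will be called, texted and emailed for three consecutive months before considered them as discontinued". No section links 6.6 to the endpoint, and none says how a gap followed by a restart is classified.

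The same item is also asked between the landmarks (6.2): at months 1, 3, 5, 7, 9 and 11 for CAB-LA, and monthly for oral.

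**The concern.** The endpoint is worded as remaining on PrEP, but the item establishes only whether the participant is on PrEP on the day of the answer. At the late landmark, one person can hold two statuses: discontinued under 6.6.1, and persistent in the primary test. An analyst who follows Section 7 as written would count that person as persistent, against both the concept in 6.2.2 and the plan's own discontinuation rule.

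The information that would show the gap is already collected, but it has no say in the classification. With 35 participants in the oral arm, one reclassified person moves that arm's proportion by 1/35 = 2.9 points. In the CAB-LA arm the step is 1/70 = 1.4 points.

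**Working it through.** **Inputs.** Discontinuation threshold: more than 3 consecutive months (6.6.1). Late landmarks: month 11 and month 12 (6.2.3, 6.2.4). Injections at months 0, 1, 3, 5, 7, 9, 11 and oral fills at months 0, 3, 6, 9, 12 (6.13.1). Arm sizes 70 and 35, with planning proportions .90 and .65 (Section 7, Sample Size). Those proportions are stated for adherence; none is given for persistence. Two assumptions are mine: missed months run from the date the next dose or fill was due, and an oral fill covers 3 months.

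**The plan's own figure.** SE = sqrt(.90 × .10/70 + .65 × .35/35) = 0.0882. The interval is .25 ± 1.96 × 0.0882 = .0771 to .4229, which matches Section 7. This point does not affect it.

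**Restarters at the late landmark.**
- Oral: a participant stops at month 4, restarts at month 9 and answers Yes at month 12. The gap is 9 − 4 = 5 months, more than 3. The person is discontinued under 6.6.1 and persistent under 6.2.4. The monthly surveys in between would record No.
- CAB-LA: injections at months 0 and 1, those due at months 3 and 5 missed, restart at month 7, Yes at month 11. The gap is 7 − 3 = 4 months, more than 3, with the same split.

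**Would the validation catch them?** A record gap of at least 91 days caps MPR at (365 − 91)/365 = 0.75, or (334 − 91)/334 = 0.73 over 11 months, if no supply is stockpiled. Restarters would therefore fall below 1.0. But so would someone one day short (364/365 = 0.997), so failing that cut-off does not identify a restarter, and no rule turns a failed MPR into a changed status.

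The sources can also disagree. If the oral participant above filled at months 0, 3 and 9, supply ran to month 6. The dispensing gap is then 9 − 6 = 3 months, which is not more than 3, while self-report shows 5.

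**Can 6.6.1 operate at month 3?** The most that can be missed by then is 3 − 1 = 2 months for CAB-LA and 3 − 0 = 3 months for oral. Neither is more than 3, so it cannot classify anyone at that landmark.

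**Sensitivity to restarters.** The counts are assumed: .90 × 70 = 63 and .65 × 35 = 22.75, rounded to 23. Restarters among those answering Yes are recounted as non-persistent.

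| Restarters CAB-LA / oral | Proportions | Difference (95% CI) | Fisher p |
|---|---|---|---|
| 0 / 0 | 0.900, 0.657 | 0.243 (0.071 to 0.415) | 0.006 |
| 0 / 3 | 0.900, 0.571 | 0.329 (0.150 to 0.507) | 0.0002 |
| 3 / 0 | 0.857, 0.657 | 0.200 (0.023 to 0.377) | 0.023 |
| 6 / 0 | 0.814, 0.657 | 0.157 (−0.025 to 0.339) | 0.091 |
| 6 / 3 | 0.814, 0.571 | 0.243 (0.055 to 0.430) | 0.011 |

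**The case against.** The strongest reply is that 6.6.1 is not an endpoint rule. No endpoint definition, outcome table or analysis paragraph applies it, and beside 6.6.2 it reads as a follow-up status rule. This stands in part. A reader might infer from 6.6.1 that early persistence is 100% in both arms by construction, or that the plan contains two competing definitions of the primary endpoint. The documents support neither: Section 7 names the measure, and that 6.6.1 cannot operate at month 3 suggests it was not meant for that landmark. It remains true that at month 11 or 12 the plan deems someone discontinued and counts the same person as persistent.

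The second reply is that claims, MPR, repeated surveys, the oral gap of more than 90 days, and missed or late injections are all in the plan. They are, and they would expose most of these cases. But the gap and the missed or late injections are adherence measures, MPR is a separate comparison, and none of them feeds back into persistence status.

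The third reply is that the endpoint and analysis wording, which speaks of remaining on or continuing PrEP, already implies continuity, so a restarter would not count. That reading is open, but the item at the landmark does not test it and Section 7 gives no instruction to look further back.

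**Conclusion.** The point holds for late persistence. Following Section 7 as written can count as persistent a participant whom 6.6.1 deems discontinued, and no rule resolves it. It deserves correction because this is a primary endpoint.

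The effect cannot be sized from the documents, which give no restart rate. The table shows only that a few participants could move the difference in either direction.

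A reader might infer that the contrast must be pulled toward no difference, because more oral users stop. With uninterrupted persistence of .90 and .65 and the same fraction r of stoppers back on PrEP in each arm, the difference does shrink by .35r − .10r = .25r, or 2.5 to 10 points for r from .10 to .40. That rests on borrowed adherence proportions, an unsourced range for r, and equal r in both arms. In general the difference shrinks only if the oral stopping proportion times its restart fraction exceeds the CAB-LA product. The documents do not establish that.

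**What to change.** Reconcile 6.2.3, 6.2.4, 6.6 and Section 7 so that one rule classifies each participant:

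- For late persistence, require a landmark Yes and no earlier gap meeting the sponsor's own 6.6.1 definition. Apply this in both arms, using the scheduled interim surveys and WVHR injection and dispensing dates. Say when a missed month starts to count.
- Keep oral bridging as persistent for CAB-LA, as in 6.2.3. A requirement that the landmark injection itself be given would contradict that section and is not proposed.
- State which source governs when self-report and records disagree, including a CAB-LA Yes with neither injection nor bridging on record.
- State that 6.6.1 does not define month-3 persistence.
- Report restarters as their own category, and give the landmark self-report proportion as a sensitivity analysis.

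This takes no position on how long a gap should count; that definition stays with the sponsor. The cost is wording and a little more analysis work, with no new data. Persistence figures may come out slightly less favourable.

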6.7. STI Screening and Management

6.7.1. Participants will receive STI screening at baseline and at every follow up clinic visit. Participants will be screened if they present with any type of symptoms that warrant STI testing. If a participant tests positive for an STI other than HIV, they will receive guideline-directed therapy at the discretion of their HCP at WVHR.

6.8. Suspected or Confirmed HIV Infection

6.8.1. HIV screening will occur a minimum as recommended for every 2 months with CAB-LA (same time as injections) and every 3 months for oral PrEP.

6.9. PrEP Choice Counselling

6.9.1. Patients will be counseled on the benefits and risks of both oral PrEP and PrEP injections. The selection of PrEP option will be done as the standard of care through shared-decision with the patient.

6.10. Possible Participant Pathways

6.10.1. There will only be two observational cohort arms. Patients will either be placed into the injectable PrEP arm or the oral PrEP arm based on their baseline prescription.

6.11. Adherence Strategies

6.11.1. Patients on oral PrEP will be encouraged to set a daily reminder on their smart phone as an alarm at the time their dose is due.

6.11.2. Patients on injectable PrEP will set a monthly calendar reminder on the day/time their injection is due.

6.12. Retention Strategies

6.12.1. Follow-up appointments will be set up and conveyed at each appointment.

6.12.2. Reminder calls will be made by a staff member a few days before the appointment.

6.13. Interventions: PrEP Initiation and Digital Health Companion Program

6.13.1. Participants will be enrolled in the CAB-LA and Oral PrEP cohorts. Participants in the CAB-LA cohort will receive their first dose of the PrEP injection at month 0. Injections will also be administered in months 1, 3, 5, 7, 9, and 11. Participants in the Oral PrEP cohort will have their prescription filled at month 0, 3, 6, 9, and 12. The schedule of dosing is presented in Figure 6a.

6.13.2. Participants in both cohorts will complete education modules and health literacy evaluations in the TheraPay App in months 2, 4, 6, 8, and 10 as presented in Figure 6a. Education Modules include PrEP Medicines (month 2), Protecting Yourself from HIV, STIs, and other infections (month 4), Building a Support System for HIV Prevention Month 6: Being an Active Participant in Your Own Care (month 8), and Overcoming Stigma and Becoming a Health Advocate (month 10).

6.14. STATISTICAL ANALYSIS

6.14.1. Study Endpoints

6.14.1.1. Medication Adherence and Persistence

Medication persistence is defined as continuing to take PrEP over time independent of adherence to the medication regimen. The proportion of

patients reporting receipt of CAB-LA or oral PrEP at months 3 (early) and end of study (late) will be measured through patient questionnaires and validation protocols. Medication adherence is defined as taking PrEP in line with medical advice.

6.14.1.2. Retention-in-Care

Retention-in-care is defined as the proportion of patients presenting for their follow-up appointments within 30 days of their scheduled visit at months 3, 9, and 12 after PrEP initiation in the oral PrEP cohort and months 3, 9, and 11 for the CAB-LA cohort.

6.14.1.3. Patient-reported Outcomes

Patient-reported outcomes will be assessed through surveys. Medication satisfaction will be measured by the HIV Treatment Satisfaction Questionnaire (HIVSTQ) adapted for PrEP and PrEP stigma will be measured by the PrEP Stigma Scale at months 1, 5, and 11. PrEP acceptance will be measured by the Modified Injection Treatment Acceptance Questionnaire (Modified I-TAQ) at months 3, 9, and 12. Barriers to adherence to oral PrEP and reasons for PrEP discontinuation will be assessed through brief behavioral surveys every month after the initiation of PrEP. Barriers to adherence to CAB-LA injections and reasons for PrEP discontinuation will be assessed through brief behavioral surveys at months 1, 3, 5, 7, 9, and 11.

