2.3. Hypothesis

2.3.1. This study is designed to test the hypothesis that, compared to oral PrEP, use of CAB-LA in underserved populations in a real-world setting supported by a digital health companion program will be associated with greater medication adherence, persistence, retention-in-care, and improved PROs.

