3. STUDY OBJECTIVES

3.1. Study Goal

3.1.1. The study will evaluate the extent to which real-world use of CAB-LA for PrEP in underserved populations impacts PrEP adherence, persistence, retention-in-care, and PROs compared with oral PrEP. Additionally, the study will examine implementation of a digital health companion program that leverages education and behavioral economics to support patients on PrEP, and assess clinician perspectives as well as barriers to, and facilitators for implementation of CAB-LA in a patient-centered medical home.

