3.3. Secondary Objectives

3.3.1. Evaluate retention-in-care in patients receiving CAB-LA vs oral PrEP

3.3.2. Evaluate PROs (including PrEP Medication Satisfaction, PrEP Acceptance, PrEP-Related Stigma, and reasons for PrEP discontinuation) in patients receiving CAB-LA vs oral PrEP

3.3.3. Evaluate the acceptability, appropriateness, and helpfulness of a digital health companion program for PrEP

[figure not shown]

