6. STUDY INTERVENTIONS AND PROCEDURES

6.1. Study Procedures and Interventions Table (Figure 6a)

CAB-LA PrEP Arm (N=70)													
Month 0	Month 0	Month 1	Month 2	Month 3	Month 4	Month 5	Month 6	Month 7	Month 8	Month 9	Month 10	Month 11	Month 12
Baseline labs and 1 st PrEP injection Baseline demographic survey	Baseline evaluation and introduction to support group	2 nd PrEP injection Persistence Assessment PRO data collection – Set #1	Education modules and health literacy evaluation	Follow-up labs and 3 rd PrEP injection PRO data collection – Set #2 Persistence Assessment	Education modules and health literacy evaluation	Follow-up labs and 4 th PrEP injection Persistence Assessment PRO data collection – Set #1	Education modules and health literacy evaluation	Follow-up labs and 5 th PrEP injection Persistence Assessment	Education modules and health literacy evaluation	Follow-up labs and 6 th PrEP injection PRO data collection – Set #2 Persistence Assessment	Education modules and health literacy evaluation	Follow-up labs and 7 th PrEP injection Persistence Assessment PRO data collection – Set #1	PRO data collection – Set #2
Oral PrEP Arm (N=35)													
Month 0	Month 0	Month 1	Month 2	Month 3	Month 4	Month 5	Month 6	Month 7	Month 8	Month 9	Month 10	Month 11	Month 12
Baseline labs and PrEP prescription filled Baseline demographic survey	Baseline evaluation and introduction to support group	Persistence Assessment PRO data collection – Set #1	Education modules and health literacy evaluation Persistence Assessment	Follow-up labs and PrEP prescription refill PRO data collection – Set #2 Persistence Assessment	Education modules and health literacy evaluation Persistence Assessment	Persistence Assessment PRO data collection – Set #1	Follow-up labs and PrEP prescription refill Education modules and health literacy evaluation Persistence Assessment	Persistence Assessment	Education modules and health literacy evaluation Persistence Assessment	Follow-up labs and PrEP prescription refill PRO data collection – Set #2 Persistence Assessment	Education modules and health literacy evaluation Persistence Assessment	Persistence Assessment PRO data collection – Set #1	Follow-up labs and PrEP prescription refill PRO data collection – Set #2 Persistence Assessment

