6.2. Description of Study Procedures

Before any screening procedure is performed, informed consent will be obtained. Labs will be taken at baseline and months 3, 5, 7, 9, and 11 for the CAB-LA cohort and at baseline and months 3, 6, 9, and 12 for the Oral PrEP cohort (only collected through standard of care). Participants will complete a baseline evaluation and be introduced to a support group at baseline. Patients will complete assessments within the TheraPay App. Clinicians will complete assessments outside of the app. Patients in both cohorts will complete baseline demographic surveys in month 0, patient reported outcomes (PRO) data collection set 1 in months 1, 5, and 11 and PRO data collection set 2 in months 3, 9, and 12. Patients in the CAB-LA PrEP cohort will complete persistence assessments in months 1, 3, 5, 7, 9, and 11. Patients in the Oral PrEP cohort will complete persistence assessments every month from months 1 through 12. Clinic staff will complete surveys at baseline, month 6, month 12, and at the end of the study. The

schedule of assessments for the CAB-LA PrEP cohort, Oral PrEP cohort, and clinicians is presented in figure 6a. Instruments are in Appendix B for the CAB-LA cohort, in Appendix C for the Oral PrEP cohort, and Appendix D for clinicians. Patient incentives for completing the assessment activities are outlined in Appendix E.

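### PrEP stigma is compared between regimens that patients help choose but is first scored at month 1, so the comparison cannot be adjusted for pre-treatment stigma

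*Combined protocol and SAP*

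**What the plan says.** **Aim.** Section 3.1 sets out to learn how far CAB-LA "impacts PrEP adherence, persistence, retention-in-care, and PROs compared with oral PrEP". The hypothesis in section 2.3 is that CAB-LA "will be associated with greater medication adherence, persistence, retention-in-care, and improved PROs". Among the secondary objectives in section 3.3, stigma is one of the outcomes compared between arms: "PrEP-Related Stigma, and reasons for PrEP discontinuation) in patients receiving CAB-LA vs oral PrEP".

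**How the arms form.** Section 6.9: "The selection of PrEP option will be done as the standard of care through shared-decision with the patient". Section 6.10 then places each patient by the baseline prescription. The Protocol Summary has the prescription written before enrolment.

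**When treatment starts.** Section 6.13.1: "Participants in the CAB-LA cohort will receive their first dose of the PrEP injection at month 0". The oral cohort's first fill is also at month 0.

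**When stigma is asked.** Section 6.14.1.3: "PrEP stigma will be measured by the PrEP Stigma Scale at months 1, 5, and 11". Section 6.2 agrees for both cohorts: patients "will complete baseline demographic surveys in month 0, patient reported outcomes (PRO) data collection set 1 in months 1, 5, and 11", and set 1 is the set that contains the stigma scale. In Figure 6a the first month-0 cell of the oral arm reads "Baseline labs and PrEP prescription filled Baseline demographic survey". A second month-0 cell lists a baseline evaluation whose content is not defined.

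**How it is analysed.** Section 7 compares baseline variables between groups and carries into multivariate models those related to persistence or adherence. It gives no method for comparing stigma scores.

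**The concern.** Stigma is a plausible influence on which regimen a patient accepts. The plan's own acceptance forms ask about hiding pills (oral arm) and hiding attendance at injection visits (CAB-LA arm). If people with more or less PrEP stigma tend towards one regimen, the arms differ in stigma before anyone is treated. The first recorded score comes after the first injection or fill, so that prior difference and any effect of the regimen are mixed in every stigma score the study collects.

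What is at stake is the interpretation of one secondary outcome: whether a CAB-LA versus oral difference in stigma can be read as the impact named in section 3.1. There may also be a smaller consequence for the main endpoints. The persistence forms list feeling judged as a reason for stopping and stigma as a challenge to continuing, yet pre-treatment stigma is not among the variables available to the models in section 7.

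**Working it through.** **1. Sequence of events**

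| Event | CAB-LA | Oral | Source |
|---|---|---|---|
| Regimen chosen and prescribed | before enrolment | before enrolment | Protocol Summary; 6.9; 6.10 |
| First injection or fill | month 0 | month 0 | 6.13.1 |
| Month-0 survey | demographic, 17 questions | demographic, 17 questions | 6.2; Appendices B, C |
| First stigma score | month 1 (second injection due) | month 1 | 6.2; 6.4.1; 6.14.1.3 |

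The Appendix H timeline, as extracted, does not show set 1 at month 1 for CAB-LA. Figure 6a, section 6.2, section 6.14.1.3 and Appendix E all do, and I follow those.

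**2. What month 0 does contain.** The baseline survey covers race/ethnicity, gender, orientation, education, coverage, housing, food, transport, safety and drug use. Questions 15 to 17 ask about everyday discrimination, the nearest construct. None of the 17 questions concerns PrEP stigma.

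**3. Which stigma items could be asked before treatment.** The scale in Part 2 of set 1 has 11 statements. Comparing Appendix B with Appendix C, two are worded to the regimen: shame about injection visits versus pills, and keeping appointments versus pills hidden. The other 11 - 2 = 9 are identical. Most concern how PrEP users are seen and need no experience of a regimen. The one on feeling proud to take PrEP comes closest to presupposing use, but a newly prescribed patient can answer it.

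**4. The plan's one design figure.** For adherence proportions of .90 and .65 with 70 and 35 patients:

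0.25 ± 1.96 × sqrt(0.90 × 0.10/70 + 0.65 × 0.35/35) = 0.25 ± 0.1729 = .0771 to .4229.

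This reproduces the Sample Size paragraph in section 7. It does not bear on stigma, for which the documents give no SD, correlation or target difference.

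**5. Illustration for stigma.** The arm sizes come from the plan. Two inputs are my assumptions: a pre-treatment difference d0 and a correlation r between the month-0 and follow-up scores. I also assume equal SDs over time, no regimen effect, no other difference between arms given the month-0 score, and response from all 105 patients.

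- SE of the unadjusted standardised difference = sqrt(1/70 + 1/35) = 0.207 SD.
- Apparent difference = r × d0. With d0 = 0.3: 0.5 × 0.3 = 0.15 SD and 0.7 × 0.3 = 0.21 SD.
- Relative to the SE: 0.15/0.207 = 0.7 and 0.21/0.207 = 1.0.
- A nominal two-sided 5% unadjusted test would then reject about 11% (r = 0.5) to 17% (r = 0.7) of the time.
- Over a wider range, d0 = 0.2 to 0.5 and r = 0.5 to 0.8, the apparent difference is 0.10 to 0.40 SD and the rejection rate 8% to 49%.
- With the month-0 score as covariate, SE × sqrt(1 - r²) = 0.179 SD at r = 0.5 and 0.148 SD at r = 0.7, ignoring the small loss from baseline imbalance itself. Under these assumptions the adjustment also removes the apparent difference, apart from measurement error in the score.

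**The case against.** The other side has several fair points.

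- **Adjustment is not ruled out.** A reader might infer that no adjusted comparison of stigma is possible. The documents do not support that: the baseline survey offers demographics, social factors and everyday discrimination. Only adjustment for earlier PrEP stigma is missing. This stands.
- **The hypothesis is worded as an association** in a study labelled an observational cohort. This stands for section 2.3, but section 3.1 asks about impact, and the missing score matters for that reading.
- **No test of stigma is specified,** and the Study Outcomes Table classes the PROs as qualitative. So the illustration describes a simple unadjusted comparison, not one the plan prescribes. This stands, although the objective is still a between-arm comparison.
- **Month 1 could serve as a reference.** The forms tell patients the questions will be repeated to see change. Change from month 1 can be computed, but it would miss any effect arising in the first month.
- **App content before month 1.** A reader might think the education programme has already shifted stigma by then. The first module is at month 2 and the stigma module at month 10, on the same schedule in both arms, so this is not part of the concern.
- **The nine common items leave out the regimen-specific worries** about hiding pills or visits, which may be the strongest link to the choice. This is a real limit on what the covariate can capture.
- **The undefined baseline evaluation** at month 0 might include stigma. No listed instrument puts it there, so the accurate statement is that none is specified.
- **The size is assumed,** and in the central illustration it is at most about one standard error. Agreed.

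**Conclusion.** The point holds in a limited form. As specified, a between-arm stigma difference at month 1, 5 or 11 cannot be adjusted for pre-treatment PrEP stigma and may partly reflect who chose which regimen. Under the assumed 0.3 SD prior difference and r of 0.5 to 0.7, that part is 0.15 to 0.21 SD, or 0.7 to 1.0 standard error at 70 versus 35 with full response. The true size cannot be known from the documents.

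Three stronger conclusions are not supported. The documents do not show that any stigma difference would be due only to selection. They do not show that stigma confounds persistence; the listed reasons for stopping make it a sensible candidate variable and no more. Nor would a month-0 score cleanly separate stigma that led to the choice from stigma that followed it, because the prescription precedes enrolment and the score would come after the choice.

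This affects one component of one secondary objective. It is still worth correcting, because the score cannot be recovered once a patient has started and collecting it costs little.

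**What to change.** 1. Add the nine stigma items common to Appendices B and C to the month-0 survey in both arms, completed before the first injection or first pill. Same-day completion is not enough unless it comes before the dose.
2. Prespecify the stigma comparison as the nine-item score at months 1, 5 and 11, adjusted for the month-0 score.
3. Report the two regimen-specific items separately by arm, since they ask different things in each.
4. Include the month-0 score among the baseline variables considered for the persistence and adherence models in section 7.
5. Report the stigma result as an association, and say that the month-0 score was taken after the regimen had been chosen.

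The cost is nine Likert items in an app survey that both arms already complete and are paid $20 for (Appendix E), plus one covariate. It needs no extra visit or procedure. The downside is a slightly longer baseline survey.
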